## 4.6.4 Frequency of hypoglycemic events using CGM data

CGM will also be utilized, based on the below specified rules, to evaluate the number of hypoglycemic episodes (number of times blood glucose falls below 70 mg/dL) and the number of severe hypoglycemic events (number of times blood glucose falls below 54 mg/dL) for each subject:

- A set of CGM readings < 70 mg/dL or <54 mg/dL, with a minimum overall duration of 15 minutes
- Up to two consecutive readings >= 70 mg/dL (or >= 54 mg/dL for separate summary) are allowed within the same episode
- If a subsequent episode starts within 60 minutes of the start of the previous episode, then they are combined and counted only as one episode

The total number (over the entire 24-hour time period) of episodes will be calculated as well as the number of nocturnal (starts during the 12 a.m. - 6 a.m. period) episodes and the number of daytime (starts during the 6 a.m. to 12 a.m.) episodes.

Baseline CGM-reported HE data will be calculated using up to 28 days of data. Baseline CGM-reported HEs will be recorded starting at Day -3 (i.e., the day prior to immunosuppression induction) and working backwards for up to 28 days (through Day -30). For instances in which the available pre-implant dataset provides <28 days of data, the dataset will be supplemented with post-implant data, using data from Day 4 forward until 28 days of data is available. Data from days on which an MMTT or SOGCT was performed, will not be included in the calculation. These

data will be used to calculate the baseline number of weekly total episodes, weekly nocturnal episodes, and weekly daytime episodes. In addition, the CGM data from the 14 days prior to each scheduled clinic visit will be used to calculate the number of weekly total episodes, the number of weekly nocturnal episodes, and the number of weekly daytime episodes for each of these visits. Data should not be used if an MMTT or SOGCT was performed on that day.

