### 7.10.4. Definition, Classification, and Management of Hypoglycemic Events (HEs)

All SMBG or CGM values of <54 mg/dL must be captured by the subject in the diary as a HE. Additionally, if a subject does not have a blood glucose value available, but has symptoms of a HE, the HE must still be captured in the diary as an HE. *For any SHE experienced between scheduled clinic visits, the subject must enter the data on the diary and also contact the study site to provide details of the event.* 

At Visit 3 (Day 1) and each clinic visit thereafter, the Investigator will review the subject's HE entries on the study diary, CGM and SMBG values, and any other supportive information. Each HE occurring beyond Visit 2 (Week -4) must be captured on a CRF and will be classified based on the definitions below. Per standards of care, the Investigator should also evaluate any HEs occurring between Visit 1 and Visit 2 reported by the subject, but they are not captured on the CRF.

- Severe hypoglycemic event (SHE): an event requiring assistance of another person to actively administer carbohydrate, glucagon, or other resuscitative actions.
- Documented symptomatic hypoglycemia: an event accompanied by typical symptoms of hypoglycemia with documented plasma glucose measured at <70 mg/dL (3.9 mmol/L).
- Asymptomatic hypoglycemia: an event with measured plasma glucose of <54 mg/dL (3.0 mmol/L) in the absence of symptoms.
- Probable symptomatic hypoglycemia: subject reports typical hypoglycemia symptoms but does not provide a temporally-associated SMBG or CGM value.
- Pseudo-hypoglycemia or relative hypoglycemia: an event is reported by subject, but the associated SMBG or CGM value is ≥70 mg/dL (3.9 mmol/L).

The frequency of HEs will be captured and counted over the course of the study. In addition, the Sponsor will consider defining additional HEs using the CGM data on an exploratory basis. The Investigator may request an Unplanned Visit to review study diary entries and determine if modifications in insulin dosing are necessary to reduce the occurrence of HEs. Based on available information, the Investigator should make appropriate decisions regarding the insulin therapy to mitigate HE occurrences.

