## 4.6.3 Frequency of hypoglycemic events using subject-reported diary data

HE data collected on the "Hypoglycemic Event" eCRF page will be used collectively for HE data summary and analysis. These data are collected from the subject-completed diaries. Hypoglycemic event logs will be completed via subject diary (via provisioned phones) by subjects. Investigators will review the hypoglycemic event logs completed by the subjects at each study visit. Blank values in the hypoglycemic events (HEs) log are considered to be 0 values.

HEs will be classified in six ways: total HEs, severe HEs, nocturnal HEs, severe nocturnal HEs, daytime HEs, and severe daytime HEs. Total HEs are HEs that occur at any time during the 24-hour period. Severe HEs (SHEs) are HEs requiring the aid of another person to administer carbohydrates, glucagon, or other resuscitative assistance any time during the 24-hour period.

Nocturnal HEs are HEs that start during the 12 a.m. - 6 a.m. period. Severe nocturnal HEs are SHEs that start during the 12 a.m. - 6 a.m. period. Daytime HEs are HEs that start during the 6 a.m. to 12 a.m. period. Severe daytime HEs are SHEs that start during the 6 a.m. to 12 a.m. period.

The baseline average weekly frequency of subject-reported HEs, SHEs, nocturnal HEs, severe nocturnal HEs, daytime HEs and severe daytime HEs will be calculated using up to 28 days of data. The baseline average weekly frequency will be calculated using data starting at Day -3 (i.e., the day prior to immunosuppression induction) and working backwards for up to 28 days (through Day -30). For instances in which the available pre-implant dataset provides <28 days of data, the dataset will be supplemented with post-implant data, using data from Day 4 forward until 28 days of data is available. Data from days on which an MMTT or SOGCT was performed will not be used in the calculation.

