#### 4.6.7 Percent of time spent with blood glucose values at various cut points

Subjects in Cohort 2 of Study VC-02-101 are required to wear their CGM, at minimum, during the 30-day period prior to their scheduled clinic visits, although wearing of the CGM for the entire two-year study is encouraged. The cut points of <54 mg/dL,  $\ge54 \text{ to } <70 \text{ mg/dL}$ ,  $\ge70 \text{ mg/dL}$  to  $\le180 \text{ mg/dL}$ , >180 mg/dL, and >250 mg/dL will be assessed. Also, severe HEs characterized by an altered mental and/or physical status requiring assistance will be summarized.

The summarization will be performed three ways: over the entire 24-hour time period, over the nocturnal (CGM value below/above the cut point occurs between 12 a.m. - 6 a.m.) time period, and over the daytime (CGM value below/above the cut point occurs between 12 a.m. - 6 a.m.) time period.

Baseline CGM data will be utilized to calculate percentages spent with blood glucose values at the various cut points for up to 28 days, starting at Day -3 (i.e., the day prior to immunosuppression induction) and working backwards for up to 28 days (through Day -30). For instances in which the available pre-implant dataset provides <28 days of data, the dataset will be supplemented with post-implant data, using data from Day 4 forward until 28 days of data is available. Data should not be used if an MMTT or SOGCT was performed on that day. In addition, the CGM data from the 14 days prior to each scheduled clinic visit will be used to calculate percentages spent with blood glucose values at the various cut points for these visits.

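### SAP 4.6.4 calls CGM episodes below 54 mg/dL severe hypoglycemic events, so the CGM run of the severe-event-free endpoint in SAP 6.2 would report a different event under the same name

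*SAP*

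**What the plan says.** **Severe defined by another person's help.** Protocol 7.10.4 defines a severe hypoglycemic event as "an event requiring assistance of another person to actively administer carbohydrate, glucagon, or other resuscitative actions", with no glucose threshold. SAP 4.6.3, for diary data, agrees: "Severe HEs (SHEs) are HEs requiring the aid of another person to administer carbohydrates, glucagon, or other resuscitative assistance". SAP 4.6.7, which deals with CGM cut points, keeps to the same idea: "severe HEs characterized by an altered mental and/or physical status requiring assistance will be summarized".

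**Severe defined by a CGM threshold.** SAP 4.6.4 counts CGM episodes below 70 mg/dL as hypoglycemic episodes. Alongside them it counts "the number of severe hypoglycemic events (number of times blood glucose falls below 54 mg/dL". An episode must last at least 15 minutes, may contain up to two consecutive readings back at or above the threshold, and is merged with another that starts within 60 minutes. Help from another person plays no part.

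**The protocol's own class for low values.** Protocol 7.10.4 has subjects enter every SMBG or CGM value below 54 mg/dL in the diary as a hypoglycemic event, not as a severe one. It defines asymptomatic hypoglycemia as "an event with measured plasma glucose of <54 mg/dL (3.0 mmol/L) in the absence of symptoms".

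**Where the label is used.** SAP 2.2.2 lists as secondary endpoints the percentage of subjects free of severe events in each between-visit interval from Week 16, and over Weeks 16 to 104. SAP 6.2 analyses them with Fisher's exact test and says this is done with diary events and with CGM events.

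**The concern.** The SAP uses one word for two different outcomes, and both feed one named endpoint. A reader who sees a percentage of subjects free of severe hypoglycemic events will take it in the protocol's sense: nobody had to step in. The CGM figure would mean something else, namely that no qualifying sensor episode below 54 mg/dL was found.

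The difference is foreseeable here. The trial enrols people with hypoglycemia unawareness or marked glycemic lability, for whom low readings without symptoms or help are an expected event type. Inclusion criterion 11 (Protocol 4.2.1) itself lists a severe event and, for CGM users, a value below 54 mg/dL as alternatives. At stake is the meaning of a reported secondary result, and the risk that two unlike percentages are read as two measurements of the same thing.

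**Working it through.** The plan states no figure to reproduce, so the check is to classify the same events under each definition and then follow the label to the analysis.

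**Step 1. Classify the same event twice.**

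| Event | Protocol 7.10.4 and SAP 4.6.3 | SAP 4.6.4 (CGM) |
|---|---|---|
| CGM below 54 mg/dL for at least 15 minutes, no symptoms, no help | Asymptomatic; not severe | Severe |
| Same CGM episode, typical symptoms, self-treated | Documented symptomatic; not severe | Severe |
| Same CGM episode, another person actively treats | Severe | Severe |
| Another person actively treats, but no qualifying CGM episode below 54 mg/dL (for example, sensor not worn) | Severe | Not counted |

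The definitions agree in one row of four. Neither set contains the other, so the CGM count is not simply a more sensitive version of the diary count. One caveat: the protocol words its symptomatic and asymptomatic classes in terms of plasma glucose. However, the same section has CGM values below 54 mg/dL entered as hypoglycemic events, so they fall within its scheme.

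**Step 2. Follow the label to the endpoint.** SAP 6.2 does not cite 4.6.4. To run the severe-event-free analysis on CGM events, a programmer needs a CGM rule for severe. SAP 4.6.3 is for diary data. SAP 4.6.7 mentions assisted events but gives no rule for finding them in sensor data, and sensor data cannot show whether someone helped. That leaves 4.6.4 as the only usable rule, so the rows marked severe in the right-hand column would decide who is counted as free.

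**Step 3. Check the observation period.** SAP 6.2 names the intervals: Weeks 16-20, 20-26, then 13-week steps to Week 104, and Weeks 16-104. It applies the same analyses to CGM. The 14-day window in 4.6.4 serves another purpose: "the CGM data from the 14 days prior to each scheduled clinic visit will be used to calculate the number of weekly total episodes". SAP 4.6.3 has the same 14-day rule for diary weekly frequencies. The natural reading is therefore the full interval for both sources.

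A confirming sentence is still worthwhile, because the two readings use very different amounts of data. With nominal visit weeks, and ignoring the excluded meal-test days, the share of each interval covered by 14-day windows would be:
- Weeks 16-20: 2/4 = 50%
- Weeks 20-26: 2/6 = 33%
- each of the six 13-week intervals: 2/13 = 15%
- Weeks 16-104: interval length 4 + 6 + 6 × 13 = 88 weeks; eight windows × 2 weeks = 16 weeks; 16/88 = 18%.

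These are shares of time, not effects on the result.

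**Step 4. Size.** Turning the definitional gap into percentage points needs the rate of assisted events and the rate of CGM episodes below 54 mg/dL. The documents give neither.

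**The case against.** The strongest reply is that nothing is hidden or merged. SAP 4.6.4 states its threshold beside the term and mostly speaks of episodes. The SAP's revision table describes diary and CGM as two separate data types, so results would be shown by source. Protocol 7.10.2 allows CGM data for secondary and exploratory endpoints and lets the SAP describe further ones. All this supports running a CGM analysis. It does not support calling the result severe when the protocol and the neighbouring SAP sections give that word another meaning.

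Three stronger readings are tempting, and the documents do not carry them.

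- *The CGM analysis cannot be reproduced because its window is undefined.* SAP 6.2 names the intervals and carries them to CGM. The 14-day rule belongs to weekly frequency, and its diary counterpart does not make the diary analysis unclear. What remains is a request for one clarifying sentence.
- *Unworn sensor time would be counted as event-free.* No passage says so. The rule that blanks mean zero, in SAP 4.6.3, is for the diary log, and SAP 4.4 allows no further imputation. Protocol 7.10.2 requires CGM use during participation. SAP 4.6.7 sets a minimum of 30 days before visits, "although wearing of the CGM for the entire two-year study is encouraged". Gaps are possible and their handling is not described; that is missing detail, not an error.
- *The protocol confines CGM-defined events to exploratory use.* Protocol 7.10.4 says only that the "Sponsor will consider defining additional HEs using the CGM data on an exploratory basis". Read with 7.10.2, an exploratory tag is partly a matter of preference. A separate title is what is needed.

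**Conclusion.** The point holds as a conflict of definitions. SAP 4.6.4 uses severe for a CGM threshold event, while Protocol 7.10.4, SAP 4.6.3 and the wording of SAP 4.6.7 reserve it for events needing another person's help. Followed as written, SAP 6.2 would report a different event under an existing secondary endpoint name. This rests on one inference: that 6.2 relies on 4.6.4 for its CGM rule. It does not say so, but no other rule is available.

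The consequence is limited. The endpoint is secondary, SAP 6.2 treats secondary p-values as descriptive, and the assistance-based diary result is reported in any case. The primary C-peptide analysis is untouched, as are the stopping and withdrawal rules, which refer to severe events in the protocol's sense. A reader might want a figure for how far the two versions would differ. Any such figure would come from assumed event rates, so none is given here.

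**What to change.** 1. In SAP 4.6.4, rename the two categories *CGM episodes <70 mg/dL* and *CGM episodes <54 mg/dL*, and drop the word severe.
2. In SAP 6.2, report the severe-event-free endpoint only from assistance-required events on the hypoglycemic event eCRF.
3. Keep the planned CGM Fisher analysis as a separately titled supportive analysis: *free of CGM episodes <54 mg/dL*.
4. As a minor clarification, add a sentence confirming that this CGM analysis uses the full between-visit intervals named in 6.2, not the 14-day windows set for weekly frequency, and show CGM wear time beside each percentage.

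The cost is SAP wording, table titles, one clarifying sentence and a wear-time entry in the CGM table. Every planned analysis is kept, and no new data are collected.

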#### 4.6.5 Clarke Hypoglycemia Unawareness Score

There is no data derivation for the Clarke Hypoglycemia Unawareness Score (the data is collected on the eCRF, and no derivation is required).

# 4.6.6 Average exogenous daily insulin dose, average exogenous weekly insulin dose, and exogenous insulin independence

Determination of exogenous insulin dosage levels and exogenous insulin independence will be determined based on the subjects' Patient Cloud recordings and not based on the investigator's case report form (eCRF) entries.

Blank values in the insulin log are not considered to be 0 values.

Exogenous daily insulin dose logs will be completed via subject diary (via provisioned phones) by subjects. Investigators will review the exogenous insulin dose logs completed by the subjects at each study visit.

#### 4.6.6.1 Daily and Weekly Exogenous Insulin Dose

Baseline average daily and average weekly exogenous insulin dose requirements will be calculated using up to 28 days of data. Baseline average daily and average weekly insulin requirements will be calculated using data starting at Day -3 (i.e., the day prior to immunosuppression induction) and working backwards for up to 28 days (through Day -30). For instances in which the available pre-implant dataset provides <28 days of data, the dataset will be supplemented with post-implant data, using data from Day 4 forward until 28 days of data is available. Data from days on which an MMTT or SOGCT was performed, will not be included in the calculation.

At Weeks 16, 26, 39, 52, 78, and 104, the last 7 daily total exogenous insulin doses recorded in the log will be used to calculate the average daily and the average weekly exogenous insulin dose at that visit. The last 7 daily records must be within the previous 14 calendar days and may not include a day in which an MMTT or SOGCT was performed. There must be at least 4 days worth of data for a particular timepoint to be considered evaluable. The weekly average value will be calculated as:

7 \* (sum of the insulin doses during the period / number of days with insulin doses in the period).

In each period, subjects must have four different days with recorded exogenous insulin doses in order for the value to be calculated.

The percent reduction in average weekly exogenous insulin dose from baseline at these visits will be calculated as:

(Average weekly insulin dose at post-baseline visit - baseline average weekly insulin dose)\*100/ baseline average weekly insulin dose.

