#### 4.2.1. Inclusion Criteria

The following inclusion criteria are applicable to all subjects:

1. Evidence of a personally signed and dated informed consent document (ICD) indicating the subject has been informed of all aspects of the trial.

- 2. Men and non-pregnant women 18-65 years of age.
- 3. Diagnosis of T1DM for a minimum of five (5) years.
- 4. Stable, optimized insulin regimen for at least 3 months. Variations in the dose of insulin are permitted and can still meet the definition of stable insulin dose (refer to the study reference manual for additional guidance on acceptable variations). Subject should be under the care of a physician using intensive insulin therapy with therapeutic goals consistent with standard of practice (e.g., American Diabetes Association guidelines) for a minimum of 6 months.
- 5. Insulin dosage at screening <1 unit/kg/day (using previous seven days as average).
- 6. The subject is an acceptable candidate for implantation and explantation of VC-02 as determined by the Surgeon and Investigator.
- 7. Willing to use the study-provided CGM system as instructed and to comply with system requirements during the trial.
- 8. Willing and able to comply with daily entries on a study diary. The subject must demonstrate compliance with daily entries on the diary between Visits 2 and 3.
- 9. Willing and able to comply with all scheduled visits, treatment plans, post-surgical care and restrictions, laboratory tests, fingerstick blood glucose monitoring, and other study procedures.
- 10. Documented hypoglycemia unawareness (Clarke score ≥4) or significant glycemic lability as assessed by the Investigator.
- 11. At least one severe hypoglycemic event, or for patients with CGMs, documentation of a low blood glucose value <54 mg/dL (<3.0 mmol/L), in the previous 12 months.
- 12. All male subjects and female subjects of childbearing potential must practice effective contraception during the study and be willing and able to continue contraception until final explant. For further details of contraceptive requirements for this study, please refer to Section 5.4.5.

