### • Anti-inflammatory (both Cohorts)

- Etanercept recommended course:
  - Day 1 (50 mg IV\*)
  - Day 4, Day 8, and Day 11 (25 mg SC)
  - \*Subcutaneous administration if required per local labeling.
- Steroids (e.g., prednisone): Recommended short-term course of steroids (e.g., approximately one-month post-implant) with a controlled taper. The overall dosing and taper period will be determined by the Investigator after consultation with the Sponsor. During the use of steroids, the Investigator should manage fluctuations in blood glucose levels in accordance with local standard of care as needed.

Additional medications can be prescribed by the Investigator to increase the safety and efficacy potential of the product after consultation with the Sponsor. As determined by the Investigator, medications and/or doses may be adjusted for safety reasons. The Investigator should refer to the applicable product labeling and package insert for details on the known and potential risks associated with the use of the immunosuppressive medications prescribed as adjunct treatment for each subject. As needed, the dosages of these medications should be adjusted to achieve the target blood concentrations (Section 7.11.3) and to minimize the potential for adverse events.

As additional data are gathered in this trial, changes in the required immunosuppressive regimen may be necessary to enhance safety and/or efficacy of VC-02. The Sponsor will notify the sites and Ethics Committee (if necessary) of such changes as information becomes available.

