# 6.2. Visit 2 / Screening (Week -4 to Week -2)

Subjects meeting eligibility criteria will return for Screening Visit 2 (Week -4). Subjects must be fasted for this visit. The following procedures will be completed:

- Review and confirm continued eligibility criteria.
- Obtain weight/vitals.
- Obtain all laboratory samples per the Schedule of Assessments.

*Note*: The immune panel blood samples may be collected at any time between Visit 2 and Visit 3, once the subject's study qualification is confirmed (Section 7.11.4).

• Perform the 4-hour MMTT. This is the baseline MMTT for efficacy evaluations.

- Dispense Continuous Glucose Monitoring (CGM) equipment and provide instructions. Insert the first sensor at the clinic. Confirm the CGM is functioning prior to the subject leaving the clinic.
- Dispense Self-Monitoring Blood Glucose (SMBG) equipment and provide instructions. Use of the meter provided by the Sponsor is required.
- Dispense the study diary and provide instructions. This is where the subject will capture insulin doses, details on HEs, and SMBG values. Remind the subject that eligibility for the trial requires daily compliance with entries between Visit 2 and 3.
- Dispense immunosuppression drugs and provide instructions for dosing (as needed).
- Assess AEs and concomitant medications.
- Contact the Sponsor to report any schedule changes or updates to the implant date.

The expected duration of the Screening Period is up to approximately five weeks. If the Enrollment Visit 3 is scheduled to occur beyond six weeks (>42 days) from the occurrence of Screening Visit 1, sites must contact the Sponsor before proceeding. Depending on the expected duration of the delay in conducting Visit 3, an Unscheduled Visit may be required to repeat certain screening procedures.

The overall Screening Period may be accelerated, but a minimum of two weeks must elapse between Visit 2 and Visit 3.

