## 7.10. Blood Glucose Monitoring

Throughout the trial, the exogenous insulin requirements of enrolled subjects are managed and titrated by the Investigator (or qualified designee) as needed to maintain glycemic control in conjunction with standards of care. For purposes of this study, the diary entries made by the subjects (e.g., insulin doses, SMBG values, and HE occurrences) are the main sources of information available to the Investigator to assist with treatment decisions. CGM data may be utilized for treatment decisions in accordance with local labeling market approvals.

In addition to Investigator review of glucose trends, insulin dosing, and HE occurrences, the Sponsor will conduct routine reviews of blood glucose data. These data are collected as part of the required study procedures. Subjects record insulin dosing and all HE occurrences on a study diary and glucometer data are electronically downloaded. The data are then available in near real-time for review. If potentially concerning trends are evidenced for an individual subject, the Sponsor will notify the Investigator and request for follow-up with the subject to occur if necessary.

Blood glucose monitoring is performed through various methods during the study to ensure proper glucose control:

- Laboratory tests (Sections 7.2, 7.3, and 7.11)
- Continuous Glucose Monitoring (Section 7.10.2)
- Self-Monitoring Blood Glucose (Section 7.10.3)

Data from these methods will be available to the Investigator via reports from laboratories, study diaries, and downloads or entries from CGM and SMBG meters to facilitate treatment decisions. The glucose monitoring data collected between Visit 2 (Week -4) and Visit 3 (Day 1) establishes the baseline profile of each subject's glycemic control (e.g., the percent time spent at various blood glucose cutpoints per CGM data, SMBG blood glucose levels, exogenous insulin doses, and frequency of HEs).

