#### 4.3 Assessment Windows

For the purpose of analyzing time to event endpoints, the time-in-study for each subject will be measured relative to Day 1, the day that the surgical procedure for VC-02-300 and/or sentinel unit implantation was attempted.

Study Visit	Target Study Day of Visit	SAP Windows		
Scheduled Study Visits for Cohort 1 and Cohort 2				
Week -4	-29	Day -36 to Day -23		
Week -3	-22	Day -22 to Day -1		
Day 1	1	Day 1		
Day 2	2	Day 2 to Day 3		
Week 2	15	Day 4 to Day 21		
Week 4	29	Day 22 to Day 42		
Week 8	57	Day 43 to Day 70		
Week 12	85	Day 71 to Day 98		
Week 16 (Cohort 1 Only)	113	Day 99 to Day 117		
Week 16 (Cohort 2 Only)	113	Day 99 to Day 126		
Week 17 (Follow-Up		Day 118 to Day 118+		
Visit: Cohort 1 Only)	120			
	Scheduled Study Visits for Col	nort 2 Only		
Week 20	141	Day 127 to Day 161		
Week 26	183	Day 162 to Day 228		
Week 39	274	Day 229 to Day 319		
Week 52	365	Day 320 to Day 410		
Week 65	456	Day 411 to Day 501		
Week 78	547	Day 502 to Day 592		
Week 91	638	Day 593 to Day 683		
Week 104	729	Day 684 to ∞		
Week 105 (Follow-Up Visit)	Last Date of Explantation + 7 Days	Not applicable		

Study visits will have windows as per the following schema:

The data will be summarized based on the electronic case report form (eCRF) (Study Visit) in which it was collected as long as the data is within the windows specified. If data for a particular Study Visit is not within the windows specified, then queries will be sent to the site to confirm data entry. ViaCyte will be notified of Study Visits that are not within the Study Visit Statistical Analysis Plan (SAP) windows. Data collected as an unscheduled visit will be re-assigned to a Study Visit based on the SAP visit windows specified.

Baseline will be defined as the last non-missing value prior to the start time of the surgical procedure for VC-02-300 and/or sentinel unit implantation, unless otherwise specified.

If more than one assessment exists within a single visit window (i.e., vital signs, laboratory samples, etc.), then the value taken closest to the target day of that visit will be used for analysis and summary purposes. In cases where two assessments are equally close to the target day, then

the first value will be used for analysis. Data from all assessments will be provided in the listing.

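### Glycemic baselines are topped up with post-implant days: 2 of 28 for a subject on schedule, 16–17 of 28 at the shortest permitted screening

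*SAP*

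**What the plan says.** The SAP's general rule in section 4.3 is pre-surgical: "Baseline will be defined as the last non-missing value prior to the start time of the surgical procedure", unless otherwise specified. Protocol 7.10 says the same for glycemic data: "The glucose monitoring data collected between Visit 2 (Week -4) and Visit 3 (Day 1) establishes the baseline profile".

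Four SAP sections specify otherwise: 4.6.3 (diary hypoglycemia), 4.6.4 (CGM hypoglycemia), 4.6.6.1 (insulin dose) and 4.6.7 (CGM time in ranges). Each takes up to 28 days, counting back from Day -3 to Day -30, and leaves out days with an MMTT or SOGCT. If fewer than 28 days are available, "the dataset will be supplemented with post-implant data, using data from Day 4 forward until 28 days of data is available". None of the four sections caps the number of borrowed days, sets a minimum number of pre-implant days, or plans a sensitivity analysis.

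The number of days available depends on Visit 2, when the diary and CGM are issued and the baseline MMTT is done (Protocol 6.2, 7.10.1, 7.10.2). SAP 4.3 gives it a target of Day -29 and a window of Day -36 to Day -23. Protocol 6.2 places it between Week -4 and Week -2, and allows screening to be accelerated provided that "a minimum of two weeks must elapse between Visit 2 and Visit 3".

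**The concern.** A baseline should describe the subject before the intervention. The SAP ends its window at Day -3 because that is the day before immunosuppression induction, then refills the window from Day 4, after both induction and surgery. For subjects given the protocol's anti-inflammatory regimen, those days fall within the steroid course: "Recommended short-term course of steroids (e.g., approximately one-month post-implant) with a controlled taper". Protocol 1.4.1 lists high blood sugar among the effects of high-dose steroids.

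The affected endpoints are change in average daily insulin dose, the proportion with a 50% insulin reduction, change in hypoglycemic event frequency (diary and CGM), and change in CGM time in range. There is no randomization (SAP 3.2.1), so change from baseline is the main reading of effect for these endpoints. The baseline enters the insulin and hypoglycemia ANCOVAs twice, in the change score and as the covariate, and it is the denominator of the insulin responder rate. The contamination also differs between subjects, because it depends on screening length and lost days.

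**Working it through.** **Inputs.** Window Day -30 to Day -3, top-up from Day 4, MMTT/SOGCT days excluded (SAP 4.6.3, 4.6.4, 4.6.6.1, 4.6.7). Data start at Visit 2, an MMTT day (Protocol 6.2, 7.10.1, 7.10.2). Target days -29 for Week -4 and -22 for Week -3 (SAP 4.3). Two-week minimum from Visit 2 to Visit 3 (Protocol 6.2): Day -15 if the SAP's target-day pattern is continued, Day -14 if 14 days are counted back from Day 1 with no Day 0.

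**The plan's own figure.** Day -30 through Day -3 is -3 - (-30) + 1 = 28 days, as stated.

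**Day count.** With Visit 2 on day V and no other days lost, the eligible pre-implant days are n = -3 - max(V + 1, -30) + 1. The borrowed days number 28 - n, run from Day 4 to Day 3 + (28 - n), and form a share s = (28 - n)/28.

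| Visit 2 | Eligible n | Borrowed | Share s | Days used |
|---|---|---|---|---|
| Day -31 or earlier | 28 | 0 | 0% | none |
| Day -30 | 27 | 1 | 3.6% | 4 |
| Day -29 (target) | 26 | 2 | 7.1% | 4–5 |
| Day -28 | 25 | 3 | 10.7% | 4–6 |
| Day -23 | 20 | 8 | 28.6% | 4–11 |
| Day -22 | 19 | 9 | 32.1% | 4–12 |
| Day -15 | 12 | 16 | 57.1% | 4–19 |
| Day -14 | 11 | 17 | 60.7% | 4–20 |

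Blank insulin days increase the borrowing, since "Blank values in the insulin log are not considered to be 0 values". Blank diary hypoglycemia entries count as zero (SAP 4.6.3), so they do not.

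**Effect on insulin endpoints.** Let r be the ratio of insulin dose on borrowed days to the pre-implant dose. The documents do not give r; the range 0.8 to 1.5 is assumed. Then:

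- baseline factor f = 1 + s(r - 1)
- apparent change when there is no true change = 1/f - 1
- true reduction that is recorded as exactly 50% = 1 - 0.5f

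For 17/28 and r = 1.5, f = 1 + 0.6071 × 0.5 = 1.304, so 1/f - 1 = -23.3% and 1 - 0.5f = 34.8%.

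| Borrowed | Baseline shift, r = 0.8 to 1.5 | True reduction recorded as 50% |
|---|---|---|
| 2/28 | -1.4% to +3.6% | 50.7% to 48.2% |
| 9/28 | -6.4% to +16.1% | 53.2% to 42.0% |
| 17/28 | -12.1% to +30.4% | 56.1% to 34.8% |

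At 17/28, a subject with no true change would show +13.8% (r = 0.8) to -23.3% (r = 1.5). With a narrower range of r = 0.8 to 1.2, the baseline shift is ±1.4% at 2/28 and ±12.1% at 17/28.

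**Precision lost without the top-up.** If days are independent, the standard error relative to 28 days is sqrt(28/n): 1.04 for n = 26, 1.21 for n = 19, 1.53 for n = 12 and 1.60 for n = 11.

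**The case against.** The best defense is that this is a deliberate trade-off. Protocol section 10 lets the SAP modify the protocol and requires an amendment only for major changes. SAP 4.3 yields where another section specifies otherwise, so the SAP does not contradict itself. The rule skips Day -2 to Day 3, reaches no further than Day 20 if no days are lost, and so stays well short of the three to six months at which graft function is expected. It gives every subject the same 28-day base, which helps most for rare severe hypoglycemia. Pre-implant days are not always free of drug effects either, because Protocol 5.2 allows immunosuppression from Visit 2. The large percentages need both a shortened screening, whose frequency is not stated, and an assumed r. No hypotheses are tested.

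Much of this stands. The borrowed days do not absorb graft effect, the on-schedule shift is small, and the count of 2 depends on conventions: Visit 2 on Day -28 gives 3, and counting the MMTT day as available gives 1. But permission to define a baseline this way does not make it a sound reference in an uncontrolled trial. The rule departs from Protocol 7.10 and undercuts the SAP's own reason for stopping at Day -3. That some pre-implant days may carry drug effects is no reason to add days that certainly follow surgery.

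**Conclusion.** The concern holds, and the rule should be changed. A subject with Visit 2 inside the protocol's Week -4 to Week -2 span, on the SAP's day numbering, needs at least 2 post-implant days. The share rises to 57–61% at the two-week minimum. It is zero only if Visit 2 falls on Day -31 or earlier, which the SAP window allows, and no other days are lost.

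The day counts follow from the documents; the size of any bias does not. It rests on the assumed r, and neither its direction nor the frequency of short screening can be settled from the text. The source of concern is surgery and adjunct drugs, not early graft function. The primary C-peptide endpoint, Clarke score, insulin independence and the percentages free of severe hypoglycemia do not use this baseline, and the p-values of the affected secondary endpoints are descriptive.

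**What to change.** In SAP 4.6.3, 4.6.4, 4.6.6.1 and 4.6.7, delete the post-implant supplementation. Average over all eligible days after Visit 2 through Day -3, keeping the Day -30 limit and the MMTT/SOGCT exclusion, and divide by the number of days available.

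State a minimum number of days and what happens to a subject below it, since SAP 4.4 allows no further imputation. Seven days, for example, would be reachable for diary data. The shortest screening still gives 11–12 eligible days, SAP 4.6.6.1 accepts 4 to 7 insulin records after baseline, and inclusion criterion 8 states: "The subject must demonstrate compliance with daily entries on the diary between Visits 2 and 3". That criterion does not cover CGM wear, so the CGM minimum needs its own check.

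Report the number of baseline days per subject, keep the topped-up version at most as a sensitivity analysis, and reconcile the text with Protocol 7.10.

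The cost is wording in four sections, reprogramming of the diary, insulin-log and CGM baselines, and the loss of precision shown above, felt most for severe hypoglycemia. The change does not remove the influence of immunosuppression started between Visit 2 and Day -3.
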